- 15. Men of childbearing potential who partner with a woman of childbearing potential, unless they agree to use effective, dual contraceptive methods (i.e., a condom, with female partner using oral, injectable, or barrier method) while on study drug and for three months following discontinuation of study drug.
- 16. Known human immunodeficiency virus or acquired immunodeficiency syndrome-related illness.

Name of Sponsor/Company: Innate Therapeutics Limited

Name of Product: MIS416

17. Serological evidence of Hepatitis B, C or HIV infection.

- 18. Any severe, acute or chronic medical or psychiatric condition or laboratory abnormality that may increase the risk associated with study participation or study drug administration, may interfere with the informed consent process and/or with compliance with the requirements of the study, or may interfere with the interpretation of study results and, in the investigator's opinion, would make the patient inappropriate for entry into this study.
- 19. Previous exposure to MIS416.

Test Product, Dose, and Mode of Administration: MIS416 is an investigational immunomodulatory agent comprised of muramyl dipeptide and single stranded bacterial DNA fragments which are cross linked together to form an insoluble microparticle. MIS416 is formulated to 0.2 mg/mL, packaged into 7 mL glass vials and heat treated at 100°C. MIS416 will be administered IV over 10 minutes beginning on Day 1 of the study, and thereafter weekly during the 28-day cycle; 4 doses will therefore constitute a cycle.

The Cohort 1 dose will be 125 μ g/week. Subsequent cohorts in the DE phase will receive, respectively, doses of up to 250, 500, and 1000 μ g/week. The decision to proceed to dosing the next cohort will be made by the Safety Review Team (see below).

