Safety: The primary endpoint is to determine the safety profile and MTD of MIS416. Assessments will include characterization of DLTs; characterization of the type, incidence, severity, timing, seriousness, and relationship to treatment of AEs; effects on vital signs and laboratory parameters; changes in electrocardiograms (ECGs) and ophthalmologic examinations; and safety MRI assessments.

Pharmacodynamics: Pharmacodynamic testing will include some or all of the following serum and cellular assays during the dose-escalation phase: Serum IFN_Y, IL-17, IL-6, TNF α and GM-CSF levels; PBMC expression of mRNA encoding IL-12p40, IL-12p35, IL-23p19, LT α , LT β , IFN_Y, IL-17, GM-CSF, ROR_Yt, and Tbet; PBMC production of IFN_Y, IL-17, and GM-CSF in response to stimulation with anti-CD3 and anti-CD28 ex vivo; PBMC production of IL-12p40, IL-12p70, IL-23, TNF α and IL-6 in response to stimulation with LPS/IFN_Y ex vivo. Depending upon findings during the dose-escalation phase, a more selective or comprehensive set of these assays will be performed during the dose-confirmation phase.

Pharmacogenomic Analysis: Following specific written consent of the subject, at least one aliquot of PBMC will be sent to [name], University of New South Wales, for genomic analysis.

Pharmacokinetics: Pharmacokinetic analysis is not applicable in this study due to the nature of MIS416 and its mode of action.

Clinical Status: Subjects will be assessed by EDSS and Multiple Sclerosis Functional Composite (MSFC)¹⁹; MRIs for clinical status will be performed at the end of the DC phase, according to a protocol to be specified in the Radiology Operations Manual.

Statistical Analysis:

Safety Analyses: Safety data analysis will be conducted on all subjects receiving at least one dose of MIS416. Analyses will consist of data summaries for clinical, biological, and PD parameters, and for AEs. The number and percentage of subjects experiencing one or more AEs will be summarized by dose level group, relationship to study drug, and severity. AEs will be coded using MedDRA terminology. Laboratory parameters will be summarized using descriptive statistics, by post-dosing shifts relative to baseline, and data listings of clinically significant abnormalities. Vital signs, ECG, and ophthalmologic examination data will be summarized by changes from baseline values at each dose

Name of Sponsor/Company: Innate Therapeutics Limited

Name of Product: MIS416

level using descriptive statistics.

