1.4.2 Repeat Dose Studies

GLP four week twice weekly and twenty six week once weekly repeated dose toxicity animal studies have been conducted to evaluate potential toxicity, look for corollaries with the protective effects of the test item previously identified *in vitro* and *in vivo*, and

Version 5

provide an estimate of No Observed Adverse Effect Level (NOAEL). The four week studies were conducted in Swiss albino mice and NZ white rabbits and the twenty six week study was conducted in NZ white rabbits.

1.4.3 4 Week Repeat Dose Studies

In mice (n=10M & 10F per group), there were were no treatment related adverse effects in the low dose group (1 mg/kg). In the mid dose group (3 mg/kg) treatment related gross pathology, an enlarged spleen, was found in one female and considered an adverse effect. Histopathology findings comprised a grade 1 lymphocytic infiltration in the urinary bladder in one female, a grade 3 histiocytic proliferation in liver in one female and grade 3 extramedullary hematopoiesis in liver in one female. These were considered adverse effects.

In the high dose group (10 mg/kg) treatment related gross pathology, enlarged spleens, were found in males and females. Histopathology findings comprised grade 1 and grade 2 lymphocytic infiltration in the urinary bladders of males and females, greater than grade 2 histiocytic proliferation in livers in males and female and greater than grade 2 extra medullary hematopoiesis in livers and spleens of males and females. These were considered adverse effects.

In view of the results NOAEL for MIS416 when administered twice weekly for 4 weeks to Swiss albino mice by i.v. route is greater than 1 mg/kg and less than 3 mg/kg bodyweight under the test conditions and doses employed.

In rabbits (n=4M & 4F per group), one death occurred in males in the high dose group (5000 μ g/kg) whereas there were no mortalities in the low and mid dose groups (50 and 500 μ g/kg respectively).

In the low dose group, desirable effects, consistent with the test items mode of action, were grade 1 histiocytic proliferation (activation of macrophages) in liver, grade 1 oval cell proliferation (activation of liver stem cell), and grade 1 bone marrow hypercellularity. Findings of grade 1 or grade 2 lymphoid hyperplasia in spleen in all males and females and grade 1 increased hemosiderous in spleen in a single female were considered treatment related but not adverse effects.

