The nature of the target for MIS416 and the mechanism of action are such that following *in vivo* administration and accumulation of the drug by the reticuloendothelial system, a transient inflammatory response can be expected. Monitoring of patient serum for increased levels of pro-inflammatory cytokines demonstrates the transient nature of MIS416 immunostimulation (Figure 1-6). These findings are very important since they demonstrate that administration of a single bolus of MIS416 does not induce an uncontrolled "cytokine storm", with maximum levels of serum cytokines peaking within 24 hour post delivery, returning to baseline levels by 48 hours.

Analysis of MIS416 - treated patient blood for a sustained inflammatory response, or the occurrence of a "second wave" of inflammatory activity over a longer time period (14 days) demonstrates there is no prolonged inflammatory activity following MIS416

Version 5

dosing. This further demonstrates that MIS416 innate immunostimulation is well controlled *in vivo* (Figure 1-7).

[figure not shown]
Figure 1-6

MIS416 systemic administration induces a transient serum inflammatory cytokine response which peaks within 24 hours following administration. Blood serum was harvested and directly measured for multiple cytokine content using flow cytometry cytokine bead array methodology (Bender MedSystem)

Version 5

Figure 1-7

MIS416 therapy does not lead to the sustained induction or a "second wave "of inflammatory mediators. Peripheral blood serum was harvested from two individual healthy donors and from a patient who had received 1 mg of MIS416 7 days prior to blood sampling. Blood serum was assayed for TNF- α , IL-6 and IL-1 β levels using flow cytometry bead array methodology.

2. Rationale for Study Design

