5.2 Exclusion Criteria

- 1. Relapsing-remitting MS or progressive-relapsing MS
- 2. Any immunomodulatory drug therapy or immunosuppressive therapy within the previous six months, or vaccine or systemic corticosteroids within the previous 60 days, prior to initiation of study drug.
- 3. Exposure to other experimental treatments currently under investigation in MS clinical trials, including alemtuzamab, rituximab, fingolimod, and cladribine.
- 4. A diagnosis or history of collagen vascular disease (including Sjögren's syndrome and systemic lupus erythematosus), anticardiolipin antibody syndrome, cerebral autosomal dominant arteriopathy with subcortical infarcts and leukoencephalopathy (CADASIL), sarcoidosis, vasculitis, Bechet's syndrome and/or Lyme disease.
- 5. History of alcohol or drug abuse (with the exception of cannabinoids) within 2 years prior to initiation of study drug.
- 6. Inability to refrain from smoking for the duration of the inpatient stay.
- 7. Major surgery or radiation therapy within 28 days prior to initiation of study drug.
- Active infection requiring antibiotics within 2 weeks prior to initiation of study drug.
- 9. Active malignancy within 2 years of entry, with the exception of basal cell carcinoma and squamous cell carcinoma of the skin
- 10. Uncontrolled congestive heart failure (New York Heart Association Classification 3 or 4 [Appendix 2]), angina, myocardial infarction, cerebrovascular accident, coronary/peripheral artery bypass graft surgery, or transient ischemic attack within 3 months prior to initiation of study drug.

- 11. Symptomatic cardiac dysrhythmias requiring treatment, or persistent prolongation of the QTcF (Frederica) interval to > 450 msec for males or > 470 msec for females.
- 12. In the Dose-Confirmation phase only, screening echocardiogram which shows abnormalities judged by the investigator to be clinically significant, including but not limited to a left ventricular ejection fraction below the testing facility's lower limit of normal.
- 13. Pregnant or lactating female.
- 14. Women of childbearing potential, unless surgically sterile for at least 3 months (i.e., tubal ligation), postmenopausal for at least 12 months (and follicle-stimulating hormone [FSH] > 20 U/mL), or unless they agree to use effective, dual contraceptive methods (i.e., oral, injectable, or barrier method with male partner using a condom) while on study drug.

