12.2.8 Pregnancy

Pregnancy occurring in the partner of a subject participating in the study, if the investigator becomes aware of it, should also be reported to the sponsor within 24 hours. A Pregnant Partner Consent Form is provided to document discussions with the partner of the study participant and to obtain her consent to collect follow up information regarding the pregnancy. The partner should be counseled regarding the possible effects to the fetus and monitoring of the subject should continue until conclusion of the pregnancy, where consent to do so is given.

13. Criteria for Premature Withdrawal

Subjects have the right to withdraw from the study at any time for any reason.

The investigator also has the right to withdraw subjects from the study in the event of intercurrent illness, AEs, protocol violations, administrative reasons or other reasons.

Should a subject decide to withdraw, all efforts should be made to complete and report the follow-up procedures, particularly the physical examination, as thoroughly as possible.

Version 5

Subjects who have prematurely withdrawn may be replaced, at the discretion of the investigators and with the approval of the sponsor, if withdrawal occurs for reasons other than DLT or an SAE related to study drug.

14. Statistical Considerations

The statistical analysis plan and biostatistical analysis is provided by Westat (Houston, TX).

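### Women's required contraception ends with study drug with no data shown to support that, and 12.2.8 states 24-hour reporting only for a partner's pregnancy

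*Protocol*

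**What the plan says.** **Contraception.** Criterion 14 ends the requirement for women of childbearing potential with the words "or barrier method with male partner using a condom) while on study drug". The Synopsis has the same rule. Criterion 15, also in both places, binds men "while on study drug and for three months following discontinuation of study drug". No other section gives women a post-dose period.

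**Persistence of the drug.** The clinical experience text in section 1 speaks of "accumulation of the drug by the reticuloendothelial system, a transient inflammatory response can be expected", and describes that response as short-lived, "with maximum levels of serum cytokines peaking within 24 hour post delivery, returning to baseline levels by 48 hours". The Synopsis states: "Pharmacokinetic analysis is not applicable in this study due to the nature of MIS416 and its mode of action". On the nonclinical side, section 1.4.1 covers acute-dose studies and section 1.4.2 says "GLP four week twice weekly and twenty six week once weekly repeated dose toxicity animal studies have been conducted". No reproductive study is described.

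**Pregnancy in the trial.** Section 12.2.8 opens with "Pregnancy occurring in the partner of a subject participating in the study" and says that this "should also be reported to the sponsor within 24 hours". The consent form that it mentions and the counselling that it asks for are for the partner. Sections 6.5.1, 6.5.2 and 6.6 schedule pregnancy testing of female subjects, where applicable, at End of Dosing and at Follow-up.

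**The concern.** There are two separate points.

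1. A woman who follows criterion 14 as written may stop contraception at her last infusion of a microparticle whose persistence in the body is not stated. She is the person directly exposed, and the text gives no reason why zero days is enough.
2. If a female subject tests positive, no sentence tells the site to inform the sponsor within 24 hours, although that duty is stated for a male subject's partner. Criterion 13 and the eligibility check at dosing visits (sections 6.3 and 6.4) should stop further dosing. What is missing is the report, and a clear duty to follow the outcome.

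Both points concern patient safety and conduct. Neither touches an estimate, a DLT count or the MTD.

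**Working it through.** The protocol has no figure of its own to reproduce here. The check is a comparison of rules and a timeline.

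**Inputs**
- Last dose: Day 22 of the final cycle, window ±1 day (section 6.3, Tables 2 to 4).
- End of Dosing: Day 29 ±2 days (sections 6.5.1 and 6.5.2). The heading of section 6.5 instead gives 7 ±1 days after the last dose.
- Follow-up: 15 days after End of Dosing (section 6.6), ±2 days (Table 2).
- Cycle length: 28 days of weekly dosing (Synopsis, Duration of Treatment).

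**Last dose to Follow-up**
- Nominal: (29 − 22) + 15 = 7 + 15 = 22 days.
- Earliest, all windows: 27 + 13 − 23 = 17 days.
- Latest, all windows: 31 + 17 − 21 = 27 days.
- Using the 6.5 heading: 6 + 13 = 19 days to 8 + 17 = 25 days.

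The Synopsis and section 4.1 place the follow-up visit 7 and 15 days after the last dose. That is a separate inconsistency and is not used here.

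**Required cover within the nominal 22 days**
- If being on study drug ends at the last infusion: 0 days covered, 22 uncovered.
- If it runs to the end of the cycle, about Day 29: 7 days covered, 22 − 7 = 15 uncovered.

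On either reading, the sponsor tests for pregnancy over an interval that the contraception rule does not fully cover.

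**Evidence on whether zero is adequate**
- For caution: accumulation in the reticuloendothelial system, no pharmacokinetic analysis, and no reproductive study in the nonclinical summary.
- For a short period: the particle is described as biodegradable (sections 1.1 to 1.3), serum cytokines are back at baseline by 48 hours, and no prolonged inflammatory activity was seen over 14 days.
- The cytokine and inflammation findings measure response. They do not show when the particle has gone. The text therefore neither supports zero nor fixes another number.

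**Search for a rule on a female subject's pregnancy**
- Section 12.2.8: the 24-hour report is tied to the partner. The word *also* presupposes a companion rule, and none is stated.
- Section 12.2.8, last sentence: it asks for the subject to be monitored to the end of the pregnancy. It sits in a sentence about counselling the partner, so whom it covers is unclear, and it sets no reporting duty.
- Section 12.2.4: congenital anomaly is a serious event, but pregnancy is not listed.
- Section 12.2.7: follow-up of adverse events and abnormal laboratory values only.
- Section 13: pregnancy is not mentioned.

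**The case against.** The strongest reply on contraception is that an eligibility rule without a printed reason is not an error. Section 12.1 refers warnings and precautions to the Investigator's Brochure. That brochure and the consent form are not available here, and either could hold the justification or further instructions. The biodegradable particle, its uptake restricted to phagocytic cells and the brief cytokine response all favour a short period. This stands in part: zero is not shown to be wrong. What remains is that the rule lacks support in the text and stops before the sponsor's own last pregnancy test.

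A reader might go further and infer that criteria 14 and 15 contradict each other, or that women need the same three months as men. The documents support neither. The two rules bind different people and can differ, and nothing shown allows the men's period to be carried over to women.

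On section 12.2.8, a reader might infer that follow-up to outcome is limited to partners. That is too strong, because the last sentence literally names the subject. It may also be said that hCG is among the safety laboratory tests (section 7.4) and that a congenital anomaly must be reported within 24 hours. Both are true, but neither is a report of a pregnancy when it is found. Lost text could in principle explain the word *also*, but the section shows no sign of a gap.

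**Conclusion.** The point holds in a limited form.

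- **Contraception:** the stated post-dose requirement for women is 0 days, or about 7 on the wider reading, while pregnancy testing continues to a nominal 22 days after the last dose (17 to 27 with all windows; 19 to 25 using the 6.5 heading). The text shown does not justify zero, and it cannot say what the right length is.
- **Reporting:** no 24-hour report is stated for a female subject's pregnancy, and the follow-up sentence is ambiguous. This is the firmer of the two points and stands whatever contraception period is chosen.

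The conclusion assumes that the current protocol text is complete on these sections and that neither the consent form nor the Investigator's Brochure already settles the matter. The number of women of childbearing potential among the planned 27 to 33 subjects is not given, so the number affected cannot be stated. It is a cheap patient-safety correction with no statistical consequence.

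**What to change.** In both copies of criterion 14, require contraception while on study drug and at least through the Follow-up visit. The sponsor should set any longer period, for example the three months used for men, from the Investigator's Brochure and give the reason.

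In section 12.2.8, state that a pregnancy in a female subject during dosing or that period is reported to the sponsor within 24 hours and followed to its outcome with her consent. Reword the last sentence so that it is clear whom it covers. Align the consent form if it does not already say this.

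The cost is a few words in two places, one sentence and one clarification in 12.2.8, and possibly a consent edit. No visits or tests are added. Some women take on a slightly longer contraception commitment. If the period runs past Follow-up, detection of a pregnancy would rest on self-report.

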5.4 Concomitant Medication

Subjects are not permitted any immunomodulatory drug therapy or immunosuppressive therapy within the previous six months, or vaccine or systemic corticosteroids within the previous 60 days, prior to initiation of study drug, or throughout the study.

Medications used to treat pre-existing conditions are permitted, provided the dose has been stable for one month prior to initiation of study drug and they must be recorded in the CRF. Medications required to treat adverse events are permitted throughout the study and must be recorded in the CRF.

5.5 Restrictions

Strenuous activity which may lead to dehydration, will not be permitted for 24 hours prior to dosing on all study days throughout the study.

Smoking and alcohol consumption will not be permitted during the inpatient stay in the unit.

Caffeine- containing food and drink will be restricted while in the unit.

6. Schedule of Assessments and Procedures

Refer to Schedule of Events:

- Table 2 DE Phase
- Table 3 DC Phase (Cycle 1)
- Table 4 DC Phase (Cycles 2 and 3)

6.1 Screening (Days -28 to -2)

Subjects who are willing to participate in the study and who have signed a Consent Form will be screened for eligibility within 28 days of dosing.

Screening tests will include a record of medical history, a physical examination (excluding breast, genital or rectal examination, unless clinically indicated), vital signs, weight, height, ECG, safety laboratory tests (haematology, biochemistry, pregnancy test and/or FSH where applicable, hepatitis B, C and HIV serology, urinalysis) and drug of abuse screen. An Expanded Disability Status Scale will be completed (see Section 9.4). A cranial MRI scan will be performed during the screening period.

Subjects who meet all of the inclusion criteria and none of the exclusion criteria will be accepted onto the study.

Documentation of the subject's fulfillment of the entry criteria, whether eligible or not, is to be completed by the investigator.

6.2 Treatment Period (Cycle 1) – Day 1

6.2.1 DE Phase Subjects

DE phase subjects will be admitted to the unit for pre-study safety blood, PD and immune parameter analysis and urine testing, pregnancy testing (if applicable), weight, vital signs, ECG and EDSS on Day 1

Subjects will undergo a physical examination (including neurological) and vital signs. Any medical history and concomitant medications taken since screening will be recorded and eligibility confirmed.

An indwelling intravenous cannula will be sited in a forearm.

A light breakfast will be consumed approximately 30 minutes prior to the scheduled dosing time.

Study drug will be drawn up in accordance with instructions in the Operations Manual and administered at the scheduled time by a slow intravenous infusion over 10 minutes. Subjects will be closely monitored for changes in their health or physiological status. At any time during dosing, the infusion rate can be reduced or the infusion turned off in response to an adverse event occurring. Once the infusion is completed, the cannula will be flushed with 0.9% sodium chloride for injection. The cannula will stay *in situ* until discharge on Day 2.

Subjects will be required to remain in bed for four hours post dose and then will be allowed to mobilise gently around the unit.

Vital signs will be repeated mid-way through the infusion (5 mins), 15 and 30 minutes, 2,4, 6, 8, 10, 12, 16, 20 and 24 hours post-dose. ECGs will be repeated 30 minutes, 1, 2, 4, 6, 8, 12 and 24 hours post-dose. Adverse event enquiry will be completed mid-way through the infusion (5 mins), 15 and 30 minutes, 2, 4, 6, 8, 10, 12, 16, 20 and 24 hours post dose and ongoing throughout the inpatient stay.

Meals, snacks and drinks will be provided throughout the day and subjects will remain overnight on the unit.

A 24-hour post-dose blood sample for PD and immune parameter sampling will be obtained the morning of Day 2 by venesection (**not via the indwelling cannula**). The cannula can be removed and the subject discharged from the unit if well.

